6.8 Immunologic Testing

To ascertain the immunologic efficacy of the prepared vaccines, several parameters will be investigated at the initiation and then again at the conclusion of the four vaccine regimen. These include *in vitro* sensitization assays to determine the development of HER-2/neu CD4⁺ and CD8⁺ T cell precursors. For each subject, immunologic evaluations on pre and post vaccination samples will be conducted simultaneously to minimize discrepancies in technique and culture conditions.

To assess the *in vivo* immunologic effects of our DC vaccine, CD4+ T and CD8+ T cells will be assessed before and after the vaccine protocol for *qualitative* evidence of HER-2/neu sensitization. In addition T cells from the sentinel node will be tested post vaccination. If this

qualitative assay demonstrates sensitization of T cells to HER-2/neu then a quantitative precursor frequency will be determined by ELISPOT analysis in order to assess the number of HER-2/neu specific T cell precursors prior to and after administration of the DC vaccine.

A. In Vitro Sensitization of Autologous CD4+ and CD8+T Cells (Optional Alternative)

Preparation of Human Lymphocyte Subsets. Pooled cryopreserved 120-140 lymphocyte cell fractions will be thawed, and separated into $CD8^+$ and $CD4^+$ T cell subsets by negative selection. T cell subset columns (R&D, Minneapolis, MN) will be used to negatively select the appropriate T lymphocyte subset by single pass over a column of glass beads coated with anti-human Ig, anti-Fc receptor antibody (CD 64) and anti-CD8 (when selecting for CD4+ T cells) or anti-CD4 (when selecting for CD8+ T cells). This method reliably enriches 90-95% for the required T cell subset while depleting the opposite T cell fraction, NK cells, B cells, and monocytes.

In Vitro Sensitization Assay. In a 24 well plate, protein- or peptide- pulsed monocytes will be plated in a 1:10 ratio with either CD4+ or CD8+ T cells and 7 days later T cell proliferation and cytokine production measured to determine if there is any primary HER-2/neu response. Macrophage Serum Free Medium (Gibco BRL, Grand Island, NY) will be used and all wells treated with GM-CSF 10ng/ml (50 IU/ml). To assess for evidence of CD4+ T cell sensitization, 100,000 CD4+ T cells will be plated alone, with an equal number of monocytes pulsed with HER-2/neu protein (20µg/ml), with 100,000 pigeon cytochrome c (PCC, 20µg/ml) pulsed monocytes and with 100,000 unpulsed monocytes. As a positive control, CD4+ T cells will also be incubated with tetanus pulsed monocytes. All groups will be run in triplicate. After incubation 37^{0} C for 5 days, thymidine, approximately $1 \Box Ci$, will be added to all wells. After at overnight incubation, the cells will be harvested onto glass fiber filtermats and assayed in a betaplate liquid scintillation counter (Wallac, Gaithersburg, MD) to determine proliferation. Additionally, to assess the cytokine profile, CD4+ T cells will be plated in a 48 well plate together with HER-2/neu pulsed monocytes, at a ratio of 1:10 using 500,000 T cells and 50,000 monocytes. After 7 days of coculture, the CD4+ T cells will be harvested and replated in new 48well plates at a 1:1 ratio with unpulsed monocytes, or monocytes pulsed with HER-2/neu or pulsed with PCC. After 24 hours, the supernatants will be harvested and tested for production of IL-2, IL-5 (as a representative Th-2 cytokine) and IFN-□ (as a marker for Th-1 type cell) by ELISA (PharMingen, San Diego, CA). CD4+ T cells will be considered sensitized to HER-2/neu if the specific proliferation or cytokine production is at least twice that of background levels (i.e. to PCC pulsed monocytes or to unpulsed monocytes).

B. Determination of HER-2/neu specific CD8+ T cells

To evaluate CD8+ T cell sensitization the CD4+ T cell proliferation and cytokine experiments described above will be duplicated, however, with the following modifications. The monocytes will be pulsed with HER-2/neu protein 20 ug/ml and then cocultured with CD8+ T cells obtained pre- and post vaccination. The T cells will be cultured for one week and tested against autologous monocytes pulsed with HER-2/neu protein or peptides and irrelevant protein or peptides and IFN- γ production measured by ELISA. T cells generated by such DC1 recognize tumor it is highly likely that the CD8+ T cells able to recognize pulsed autologous monocytes can recognize endogenous HER-2/neu on tumor cells. In HLA.A2.1 subjects, which we expect

to be about 25% of the total subjects, monocytes will be pulsed with either the HER-2/neu peptide (369-77) or an irrelevant melanoma and colon peptides. Proliferation of CD8+ T cells to the flu peptide will be utilized as the positive control. We will further evaluate CD8+ T cells sensitization to HER-2/neu epitopes using HLA.A2.1 positive, HER-2/neu expressing tumor cell lines and negative controls. Proliferation assays and IFN- roduption by CD8+ T cells to HER-2/neu positive and negative tumor cell lines will be tested. Subjects not HLA-A2+ or HLA-A3+ will have their HLA class I typing and attempt to find matched breast cancer cell lines that are HER-2/neu over-expressing and non-expressing to demonstrate specific tumor recognition.

C. ELISPOT Analysis

To *quantitatively* determine whether the levels of circulating, HER-2/neu specific CD4+ and $CD8^+$ T cells, precursors are increased with vaccination therapy, ELISPOT analysis will be performed on the subjects pre- and post vaccine T cells. As before, CD 4+ and CD8⁺ T cells will be obtained from subjects through leukapheresis prior to administration of vaccines and again after all six injections have been delivered and the assays run at the conclusion of the trial. As with the sensitization studies, monocytes are pulsed with protein or peptide and cocultured with T cells at 10:1 T cell to monocyte ratio. After 7 days the T cells will be harvested and restimulated with antigen presenting cells pulsed with relevant and irrelevant protein in ELISPOT plates.

The ELISPOT plate will be prepared by coating Millipore plates with nitrocellulose membranes with 10 ug/ml anti-human IFN- γ or IL-5. The plates will be coated at 4° C overnight and unbound antibody will be removed with washing with PBS. The plates will be blocked with RPMI/10% heat-inactivated human AB serum for 1 hour at 37° C. Harvested T cells 10⁵ will be added in triplicate and HER-2/neu pulsed and irrelevant pulsed monocytes will be added at 1:10 ratio with T cells in a final volume of 200 ul. Cells will be cocultured for 24 hours and cells will then be removed by washing six times with PBS/0.05% Tween 20. Captured cytokine will be detected by incubation for 2 hours at 37° C with biotinylated mAb anti-IFN- γ or anti-IL-5 in PBS/0.5% BSA. The wells will be washed again six times with PBS/Tween, then Avidan-Peroxidase Complex will be added 1 hour at room temperature. Unbound complex will be washed with 3 washes PBS/Tween then 3 washes PBS. Peroxidase staining will be performed with 3-amino-9-ethyl-carbozole for 4 minutes and stopped by placing the plates under tap water. Spot numbers will be determined with an automatic ELISPOT reader that is to be purchased and the accompanying computer software. Spots from well with relevant vs. irrelevant protein pulsed APC will be compared and precursor frequency will be estimated.

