6.9 Statistical Considerations

6.9.1 Design. A single arm phase I trial of HER-2 pulsed DC1 vaccine in subjects with high risk HER-2^{pos} breast cancer with residual disease after neoadjuvant therapy. Subjects will receive 6 weekly DC1 vaccinations and may then be eligible to receive up to 3 boost vaccinations given every 3 months. This study will enroll 18 evaluable subjects. Evaluable implies that a subject received all 6 weekly vaccinations and underwent leukapheresis after the vaccinations for immune response evaluation. Subjects will be followed for 30 days after their *final* vaccination.

6.9.2 Objectives. The primary objectives are to determine feasibility and safety. The secondary objectives are to evaluate immunogenicity and anti-HER2 immunity.

6.9.3 Endpoints. Feasibility is defined as a subject's ability and willingness to complete the treatment regimen (6 weekly vaccinations). Safety is established by grading the observed toxicities using CTC Version 3.0. Cardiac toxicity due to trastuzumab will be monitored 2 weeks after the sixth weekly vaccination (week 8) and at EOS and scored separately from vaccinerelated toxicity. Cardiac toxicity is defined as either asymptomatic change in MUGA (i.e., >20% decline in EF by repeat echo or EF <50%) or symptomatic EF drop or heart failure. Doselimiting toxicity (DLT) due to vaccination is defined as: Grade 2 allergic reaction/generalized urticaria, > Grade 3 allergic reaction/other, > Grade 2 autoimmune reaction, > Grade 2 cardiac toxicity or as specified above, > Grade 3 hematologic and non-hematologic toxicity (except fever) and > Grade 2 toxicity due to leukapheresis. DLT rate will be defined by the weekly vaccination schedule. Toxicities will be scored separately for the maintenance boost schedule. Immunogenicity is evaluated with descriptive statistics and box plots for multiple CD4+ and CD8+ T cell metrics obtained at baseline, 2 weeks after the sixth weekly vaccination (week 8) and after each maintenance boost, as show in the table below. Immune response (IR) is defined as >2 fold increase relative to baseline. Anti-HER2 response will be a quantitated by dilution studies. Long-term anti-HER2 immunity will be assessed at follow-up visits (e.g., q 6 months).

Immune Parameter	Assay Method	Fold change	Response (>2 fold ↑)
Peptide specific reactivities	Tetramer	~	\checkmark
CD8+ T cell activation or tumor recognition	cytokine release	~	\checkmark

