CD4+ T cell activation	ELISPOT	~	\checkmark
Overall immune response	(response to any of a	above)	

6.9.4 Monitoring Unacceptable Toxicity. Early termination rules for asymptomatic and symptomatic cardiac toxicity and vaccine-related dose-limiting toxicity have been defined for monitoring purposes. Toxicity data will likely be reviewed after groups of 3 women have been treated. Enrollment will be terminated if data indicate that the rate of 1) asymptomatic cardiac toxicity >20%, 2) symptomatic cardiac toxicity/heart failure >5% or 3) vaccine-related DLT rate >25%. For cardiac toxicity, we assume an uninformative beta (1, 1) prior and for vaccine-related DLT we assume a modestly informative beta (1, 3) prior since safety of our DC1 vaccine has been established in >50 women treated on our DCIS trials. Given the prior and the observed data, the Bayesian posterior probability that the toxicity rate exceeds the specified rate, is calculated. If the numbers of subjects with toxicity equals or exceeds the numbers (in shaded rows) in the table below, then it is likely that the toxicity rate is unacceptable, as noted by Bayesian posterior probabilities.

Bayesian Early Termination Rules for Cardiac Toxicity Rate							
Subjects treated	3	6	9	12			
Subjects with asymptomatic cardiac toxicity	1	2	3	4			
Bayesian Posterior Prob[tox rate >20%]	0.82	0.85	0.88	0.90			
Subjects with symptomatic cardiac toxicity/heart failure	1	1	1	1			
Bayesian Posterior Prob[tox rate >5%]	>0.9	>0.9	0.91	0.86			

Subjects with vaccine-related DLT	2	3	4	5
Bayesian Posterior Prob[DLT rate >25%]	0.83	0.83	0.84	0.85
Action	Terminat	te accrual	, re-evalu	ate trial

6.9.5 Statistical Analyses and End of Trial Decision-making. Feasibility. A narrative of reasons why subjects could not complete treatment will be written. Safety. All graded toxicities will be tabled and described by frequency and percentage. Attribution to DC1 vaccine or trastuzumab will be assigned, if possible. All cardiac toxicities will be reported in detail. Toxicities observed during weekly vaccination will be tabled separately from toxicities observed during maintenance boosts. **Immunogenicity**. Immunogenicity will be evaluated by descriptive statistics, plots of pre- and post-treatment values and fold changes. Immune response rate and 95% exact confidence interval will be calculated. Anti-HER2 response will be quantitated as EOS/baseline fold change in dilution studies.

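### Section 6.8 makes ELISPOT conditional on a positive qualitative assay, 6.8.C does not, and 6.9 does not say how an untested subject counts in the CD4 response

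*Combined protocol and SAP*

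**What the plan says.** The relevant text of the combined protocol and SAP is in sections 6.8 and 6.9.

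- **6.8, introduction.** ELISPOT follows a positive qualitative result: "qualitative assay demonstrates sensitization of T cells to HER-2/neu then a quantitative precursor frequency will be determined by ELISPOT analysis". The qualitative step covers both subsets and both times: "CD4+ T and CD8+ T cells will be assessed before and after the vaccine protocol". It is not stated which subset, or which of the two samples, has to be positive.
- **6.8.A.** The heading of the qualitative assay reads "In Vitro Sensitization of Autologous CD4+ and CD8+T Cells (Optional Alternative". Its threshold for CD4 is "CD4+ T cells will be considered sensitized to HER-2/neu if the specific proliferation or cytokine production is at least twice that of background levels".
- **6.8.C.** Here the condition is absent: "ELISPOT analysis will be performed on the subjects pre- and post vaccine T cells". Cells are taken before vaccination and "again after all six injections have been delivered and the assays run at the conclusion of the trial".
- **6.9.3.** "Immune response (IR) is defined as >2 fold increase relative to baseline". The accompanying table assigns ELISPOT to CD4 activation, cytokine release to CD8 activation or tumor recognition, and tetramer to peptide reactivity. Overall response is a response on any of the three.
- **6.9.5.** "Immune response rate and 95% exact confidence interval will be calculated". Fold changes are also to be described and plotted. No denominator is named, and there is no rule for a subject without an assay result.
- **6.9.1.** A subject is evaluable after all six vaccinations and a post-vaccine leukapheresis. The qualitative assay plays no part in this definition.

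**The concern.** Under the introduction to 6.8, a subject with a negative qualitative assay has no ELISPOT values and so no CD4 fold change. The gate is closely related to the endpoint: it measures HER-2-specific proliferation or cytokine production, and ELISPOT counts cytokine-secreting cells after a similar seven-day co-culture. Subjects removed by the gate are therefore likely to be those with the smallest responses.

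Two summaries are exposed. The CD4 fold-change statistics and plots can use only subjects with values, so they are selected whenever the gate is applied. The CD4 response rate is selected only if untested subjects are also left out of the denominator, which 6.9 neither requires nor rules out.

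At stake is how strongly the trial appears to show immune activity. Section 10.0 makes follow-on trials depend on safety and on the generation of immune responses, and the background stresses CD4 cells. The assays are run at the end of the trial, so unless the text settles the question beforehand, the choice could be made once results begin to appear.

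**Working it through.** The plan gives no expected immune response rate, power or sample size for this endpoint, so there is no figure of its own to reproduce. What can be checked is how far the unresolved choice moves the result.

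**Inputs**

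- N = 18 evaluable subjects (6.9.1). Section 6.9.6 says 17, so both are shown.
- g = number passing the gate, which is an assumption. The nearest figure is the 85-90% induction rate in 5.3: 0.85 × 18 = 15.3 and 0.90 × 18 = 16.2, so 15 or 16 subjects. Those earlier patients had not just had chemotherapy or trastuzumab, whereas this trial's subjects have completed such treatment. Smaller values of g are therefore shown too.
- x = ELISPOT responders among those passing, also an assumption.

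**Formulas**

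- Rate among tested subjects only = x/g.
- Rate with untested subjects counted as non-responders = x/N.
- Intervals are exact (Clopper-Pearson) 95%, the type named in 6.9.5.

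**Results for N = 18**

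| Pass (g) | Respond (x) | x/g (95% CI) | x/18 (95% CI) | Difference (points) |
|---|---|---|---|---|
| 16 | 14 | 87.5% (61.7-98.4) | 77.8% (52.4-93.6) | 9.7 |
| 15 | 13 | 86.7% (59.5-98.3) | 72.2% (46.5-90.3) | 14.4 |
| 12 | 10 | 83.3% (51.6-97.9) | 55.6% (30.8-78.5) | 27.8 |
| 9 | 8 | 88.9% (51.8-99.7) | 44.4% (21.5-69.2) | 44.4 |

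With N = 17, the all-evaluable rates are 82.4%, 76.5%, 58.8% and 47.1%. The first two differences become 87.5 − 82.4 = 5.1 and 86.7 − 76.5 = 10.2 points.

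**Direction.** Suppose r of the N − g untested subjects would have responded if tested. The rate with everyone tested is (x + r)/N. Then x/g exceeds (x + r)/N exactly when x/g > r/(N − g), that is, when response is more common among those passing the gate than among those failing it. The table takes r = 0. In its first row, r = 1 gives 15/18 = 83.3%, a difference of 87.5 − 83.3 = 4.2 points, and r = 2 gives 16/18 = 88.9%, so the tested-only rate would be 1.4 points too low.

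The same algebra shows the cost of scoring untested subjects as non-responders: the rate falls short by r/N, or 1/18 = 5.6 points for each such subject who would have responded.

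**The case against.** The strongest reply is that the plan, read as a whole, is not a gated design. The section devoted to ELISPOT states no condition, the gating assay is labelled optional, and an optional assay cannot dependably control entry to a planned endpoint. Section 6.9 never mentions the gate, and its definition of evaluable points to a denominator of 17 or 18 whatever the qualitative result.

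Much of this stands. A reader might infer that ELISPOT will be run only in sensitized subjects, and that the response rate will be computed among subjects already known to have responded. The documents do not support that reading, for three reasons:

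- 6.8.C contradicts the first half of it.
- No text removes gate-negative subjects from the denominator.
- Passing the gate is not responding. The CD4 gate is a multiple of background, while response is a rise from baseline. A subject sensitized before vaccination could pass without any vaccine response. If the gate were read on the pre-vaccine sample, its link to a later rise could be weak, and even the direction of bias would be uncertain.

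It is also fair to say that immunogenicity is secondary and descriptive in 6.9.2 and 6.9.5, that tetramer and cytokine release feed the overall response as well, and that the sizes above rest on assumed counts.

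The reply does not remove the condition from the introduction to 6.8, which is a stated rule and not merely missing detail. Nor does the definition of evaluable say how an evaluable subject with no ELISPOT value is scored, and it cannot supply a fold change that was never measured.

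**Conclusion.** The point holds as a conflict between two parts of section 6.8 together with a gap in 6.9. If the condition is followed, CD4 fold-change summaries come from subjects selected on a correlate of response, and so does the CD4 response rate if untested subjects are dropped. The expected bias is upward, provided that response is more common among those who pass the gate.

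Under the assumed counts, the rate is overstated by about 10 to 14 points if 15 or 16 of 18 pass, and by about 28 to 44 points if 9 to 12 pass. These sizes assume that no untested subject would have responded and shrink if some would have. With 17 evaluable subjects the first range is about 5 to 10 points.

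The effect is on interpretation of one of three immune parameters. It also reaches the overall response, because that counts a response on any of them. No power calculation, error rate or toxicity stopping rule changes. The correction should be made before the assays are run.

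**What to change.** - In the introduction to 6.8, delete the condition so that it agrees with 6.8.C, and state that paired pre- and post-vaccine ELISPOT is run on every evaluable subject regardless of the qualitative result.
- In 6.9.5, name all evaluable subjects as the denominator for the CD4 response rate and its exact interval, and report the number actually tested. Reconcile the 17 and 18 in 6.9.6 and 6.9.1 at the same time.
- If an evaluable subject is nevertheless untested, show the rate with that subject counted as a non-responder, and say that this can bias the rate downward. This is a disclosed fallback, not a substitute for testing.

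The cost is a small number of extra assays. Section 6.1.1 and Appendix 1 treat the post-vaccine leukapheresis as optional, but an evaluable subject has had one by definition, and pre-vaccine cells come from the collection made before vaccination. No new procedure is needed for these subjects.

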6.9 Statistical Considerations

6.9.1 Design. A single arm phase I trial of HER-2 pulsed DC1 vaccine in subjects with high risk HER-2^{pos} breast cancer with residual disease after neoadjuvant therapy. Subjects will receive 6 weekly DC1 vaccinations and may then be eligible to receive up to 3 boost vaccinations given every 3 months. This study will enroll 18 evaluable subjects. Evaluable implies that a subject received all 6 weekly vaccinations and underwent leukapheresis after the vaccinations for immune response evaluation. Subjects will be followed for 30 days after their *final* vaccination.

6.9.2 Objectives. The primary objectives are to determine feasibility and safety. The secondary objectives are to evaluate immunogenicity and anti-HER2 immunity.

6.9.3 Endpoints. Feasibility is defined as a subject's ability and willingness to complete the treatment regimen (6 weekly vaccinations). Safety is established by grading the observed toxicities using CTC Version 3.0. Cardiac toxicity due to trastuzumab will be monitored 2 weeks after the sixth weekly vaccination (week 8) and at EOS and scored separately from vaccinerelated toxicity. Cardiac toxicity is defined as either asymptomatic change in MUGA (i.e., >20% decline in EF by repeat echo or EF <50%) or symptomatic EF drop or heart failure. Doselimiting toxicity (DLT) due to vaccination is defined as: Grade 2 allergic reaction/generalized urticaria, > Grade 3 allergic reaction/other, > Grade 2 autoimmune reaction, > Grade 2 cardiac toxicity or as specified above, > Grade 3 hematologic and non-hematologic toxicity (except fever) and > Grade 2 toxicity due to leukapheresis. DLT rate will be defined by the weekly vaccination schedule. Toxicities will be scored separately for the maintenance boost schedule. Immunogenicity is evaluated with descriptive statistics and box plots for multiple CD4+ and CD8+ T cell metrics obtained at baseline, 2 weeks after the sixth weekly vaccination (week 8) and after each maintenance boost, as show in the table below. Immune response (IR) is defined as >2 fold increase relative to baseline. Anti-HER2 response will be a quantitated by dilution studies. Long-term anti-HER2 immunity will be assessed at follow-up visits (e.g., q 6 months).

Immune Parameter	Assay Method	Fold change	Response (>2 fold ↑)
Peptide specific reactivities	Tetramer	~	\checkmark
CD8+ T cell activation or tumor recognition	cytokine release	~	\checkmark
CD4+ T cell activation	ELISPOT	~	\checkmark
Overall immune response	(response to any of a	above)	

6.9.4 Monitoring Unacceptable Toxicity. Early termination rules for asymptomatic and symptomatic cardiac toxicity and vaccine-related dose-limiting toxicity have been defined for monitoring purposes. Toxicity data will likely be reviewed after groups of 3 women have been treated. Enrollment will be terminated if data indicate that the rate of 1) asymptomatic cardiac toxicity >20%, 2) symptomatic cardiac toxicity/heart failure >5% or 3) vaccine-related DLT rate >25%. For cardiac toxicity, we assume an uninformative beta (1, 1) prior and for vaccine-related DLT we assume a modestly informative beta (1, 3) prior since safety of our DC1 vaccine has been established in >50 women treated on our DCIS trials. Given the prior and the observed data, the Bayesian posterior probability that the toxicity rate exceeds the specified rate, is calculated. If the numbers of subjects with toxicity equals or exceeds the numbers (in shaded rows) in the table below, then it is likely that the toxicity rate is unacceptable, as noted by Bayesian posterior probabilities.

Bayesian Early Termination Rules for Cardiac Toxicity Rate							
Subjects treated	3	6	9	12			
Subjects with asymptomatic cardiac toxicity	1	2	3	4			
Bayesian Posterior Prob[tox rate >20%]	0.82	0.85	0.88	0.90			
Subjects with symptomatic cardiac toxicity/heart failure	1	1	1	1			
Bayesian Posterior Prob[tox rate >5%]	>0.9	>0.9	0.91	0.86			

Subjects with vaccine-related DLT	2	3	4	5
Bayesian Posterior Prob[DLT rate >25%]	0.83	0.83	0.84	0.85
Action	Terminat	te accrual	, re-evalu	ate trial

6.9.5 Statistical Analyses and End of Trial Decision-making. Feasibility. A narrative of reasons why subjects could not complete treatment will be written. Safety. All graded toxicities will be tabled and described by frequency and percentage. Attribution to DC1 vaccine or trastuzumab will be assigned, if possible. All cardiac toxicities will be reported in detail. Toxicities observed during weekly vaccination will be tabled separately from toxicities observed during maintenance boosts. **Immunogenicity**. Immunogenicity will be evaluated by descriptive statistics, plots of pre- and post-treatment values and fold changes. Immune response rate and 95% exact confidence interval will be calculated. Anti-HER2 response will be quantitated as EOS/baseline fold change in dilution studies.

6.9.6 Sample Size Justification and Study Duration. This phase I trial will enroll 17 evaluable subjects over 1.5 years and will firmly establish feasibility and safety of DC1 vaccination. In addition to Bayesian posterior probabilities for toxicities, binomial probability statements will also inform our decision-making. For example, a treatment may be considered excessively toxic if \geq 3 of 15 subjects exhibit unacceptable vaccine-related toxicity. This rule yields at least 0.76 probability of correctly judging the treatment as excessively toxic if the true toxicity rate is >25%, with no more than 0.18 probability of incorrectly judging the treatment as excessively toxic if the true toxicity rate is <10%.

